# C. Have stopping rules been established for the study (to evaluate whether the objectives have been met, or that the objectives cannot be met, or that the accumulated data indicates that the risks exceed the benefits of the study)?

#### □No ⊠ Yes □ N/A (study is not greater than minimal risk)

If YES, describe the stopping rules: The study will be stopped so the protocol can be re-evaluated for the following reasons: (1) catheter-related bloodstream infections identified in > 5 patients per arm (~15% of cohort), (2) catheter related venous thromboembolism identified in > 5 patients per arm (~15% of cohort), (3) catheter failure rate (meaning catheter had to be removed prior to completion of therapy intended for) > 50%, (4) cross-over rate > 30%. Those stopping rules will be assessed continuously from the time first patient is enrolled until study completion.

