#### Preliminary work and results

We are one of the first few pediatric hospitals in the United States to implement and describe the development of an LPC program.[6] The LPC program was introduced at Children's Wisconsin (CW) in 2019 and was subsequently initiated in the intensive care units. In October 2021 the program expanded to the rest of the hospital. Our ability to place LPCs in hospitalized children gives us a significant advantage in obtaining high quality evidence regarding LPC use in pediatrics. In our initial test group of 20 successfully placed LPCs, there were no major complications such as VTE or CLABSI (*Table 2*). We did identify a 25% dislodgement rate that we are working to reduce by improving the LPC securement.

LPCs inserted (n)	20
Patients (n)	19
Age (years) median (IQR)	11 (7-15)
Male, n (%)	9 (45%)
Location, n (%)	
Acute Care unit	9 (45%)
Intensive Care unit	11 (55%)
Service, n (%)	
Critical Care	7 (35%)
Gastroenterology	6 (30%)
Hospital Medicine	4 (20%)
Oncology	3 (15%)
Anatomic Site, n (%)	
Cephalic vein	7 (35%)
Basilic vein	12 (60%)
Brachial vein	1 (5%)
Number of insertion attempts, n (%)	
1 attempt	19 (95%)
2 attempts	1 (5%)
Catheter size	
22 gauge	10 (50%)
20 gauge	10 (50%)
PIV insertion attempts prior to LPC.*n (%)	
0 attempts	12 (60%)
1 attempt	4 (20%)
2 attempts	3 (15%)
3 attempts	1(5%)
LPC Duration, days, median (IQR)	5.5 (1-9)
Remained until therapy completion, n (%)	11 (55%)
Complications, n (% )	
Occlusion	2 (10%)
Dislodgement	5 (25%)
Phlebitis	0 (0%)
Venous Thromboembolism	0 (0%)
Central Line Associated Blood Stream	0 (0%)
Infections	

Since the initial pilot of the LPC program, 43 LPCs have been placed at CW as standard of care (up until November 2021, see figure below). All LPCs were placed in the upper extremity (77% in the upper arm); 88% were placed in the PICU. The median (IQR) dwell-time was 6 (3-11) days; 14% remained in for > 14 days (max dwell-time 41 days), 19% for 7-14 days, and 58% for  $\leq$ 7 days. Reason for removal was "no longer medically needed" in 70% (n=30) of the LPCs and complications in 21% (n=9). Most frequent complication was occlusion (n=3) and infiltration (n=2). These complications are similar to those of a peripheral IV. No clots or line infections identified.

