#### E. Design and methods (including experimental design, technical details and laboratory methodology):

#### Study design:

Randomized clinical trial. We propose a parallel group, pragmatic randomized non-inferiority pilot trial design (*arm 1* and *arm 2*) (**Figure 1 below**) assessing the feasibility of a full-scale effectiveness trial comparing PICCs to LPCs for non-central, medium-term vascular access (5-14 days) in pediatrics.

Mixed methods (qualitative and quantitative data) will be used to determine patient/family experience.

**Setting and sample:** This single center pilot study will take place at Children's Wisconsin main hospital in Milwaukee. We plan to use convenience sampling, enrolling Monday through Friday 8-5pm during the one-year timeline.

Inclusion criteria: patients age 2 to 17 years admitted to Children's Wisconsin and requesting placement of a PICC () for: (1) anticipated length of intravenous treatment of 5-14 days, (2) planning peripherally compatible infusates [28] (3) VAD not needed at discharge.

Exclusion criteria: non-English-speaking family, active bacteremia or VTE at site where device would be placed, urgent need of vascular access (within 4 hours), another central venous catheter already in place, device needed for any intervention requiring central access such as medications that cannot be given peripherally OR central monitoring. To be included in the study, the treating attending physician will need to give approval for participation and randomization.

Inclusion/Exclusion criteria for guardian participation in the semi-structured interviews: > 18 years old, English speaking.

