	(a) the risk is justified by the anticipated benefit to the subjects (for each group): Using comparative effectiveness research design, we aim to compare two VADs used in hospitalized pediatric patients (PICCs vs LPCs), both of which are currently available for routine care at CW. Even if not enrolled in the study, the study participants would require the placement of a VAD (PICC) for delivery of therapies such as IV fluids or antibiotics. (1)PICC (control) group: This group is receiving the VAD that the primary medical team planned to use for prolonged medical therapy (5-14 days). Because a PICC line is a central line, in rare situations (3-4% of cases)[7] a serious complication such as blood stream infection or clot can develop. Those complications require medical treatment (e.g., anticoagulation or antibiotics) and VAD removal. PICCs have other complications that are more minor such as occlusion, dislodgment, mechanical failure that if were to happen would require replacement of the VAD. PICCs generally are placed under sedation with the additional risk of sedation related complications (nausea/vomiting) and require an XR to confirm tip location. However, the anticipated benefits of using a PICC are many. The PICC stays in for weeks to months, so the medical therapy is not interrupted, in general no extra VADs are needed because PICCs have an 80-90% completion of therapy. By staying in longer, extra pokes for additional VADs are avoided. PICCs can also be used for blood draws, so additional pokes for blood draws are avoided. (2) LPC (interventional) group: LPCs are peripheral VADs similarly to a traditional PIV secause they are longer (catheter length 8 cm vs traditional PIV < 4 cm) they last longer (>5 days LPC vs 2-3 days PIV). The most common complications for an LPC are dislodgment, occlusion, infiltration which would require the replacement of the VAD. LPCs can be used for blood draws before they would clog. LPCs are more cost effective as compare to PICCs. For the pain/anxiety scales assessing VAD p
L Forn	answering mese questions is me same as what is typically asked about in routine examination n Version Date: 02/24/2020
rorn	in version Date: 02/24/2020 CW Protocol Summary Page 22 of 30

during medical treatment and care.

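### Stopping rules 3 (catheter failure above 50%) and 4 (cross-over above 30%) run from the first patient with no minimum number and no stated base, so one early event can halt the pilot for re-evaluation

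*Combined protocol and SAP*

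**What the plan says.** Section 6 C gives the consequence of any trigger: "The study will be stopped so the protocol can be re-evaluated". Rules 1 and 2 (bloodstream infection, thromboembolism) are counts, more than 5 patients per arm. Rules 3 and 4 are bare rates: "catheter failure rate (meaning catheter had to be removed prior to completion of therapy intended for) > 50%, (4) cross-over rate > 30" (the last figure is a percentage). The timing clause covers all four: "Those stopping rules will be assessed continuously from the time first patient is enrolled until study completion".

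Other places that bear on the point:

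- Section 6 A and B: there is no DSMB. Complications are followed daily, and a safety assessment of complication, failure and cross-over rates is scheduled after 20 and after 40 of the 70 participants.
- Section 6 D: cross-over is a proportion of subjects leaving their randomized device in any direction, without saying per arm or pooled. Section 1, Risks, B mentions the LPC-to-PICC direction only.
- Section 1, Study Design, E: patients have an "anticipated length of intravenous treatment of 5-14 days", with the centre "enrolling Monday through Friday 8-5pm during the one-year timeline".
- Failure rates: Section 8 E says "PICCs have an 80-90% completion of therapy". In Section 1, Study Design, D, Table 2, the line "Remained until therapy completion" shows 11 of 20 LPCs. A later series of 43 LPCs lists 9 removals (21%) for complications.

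**The concern.** A running percentage over one, two or three patients is almost all noise, yet crossing the line here is not advisory: the text requires a stop. The pilot has one centre and one year, so a halt caused by the order of the first few outcomes could cost enrolment time without telling anyone much about the devices.

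The base is also undefined. Rules 1 and 2 say per arm; rules 3 and 4 do not. For failure, the text does not say whether the denominator is patients enrolled or devices with a known outcome. Two careful readers could therefore operate materially different rules. Pooling can also hide a poor arm: with assumed failure of 70% on LPC and 15% on PICC, the pooled rate is (70 + 15)/2 = 42.5%, below the threshold.

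**Working it through.** **The plan's own figure.** Rules 1 and 2 gloss 5 patients as about 15%. 5/35 = 14.3% and 5/70 = 7.1%, so that gloss works only with the 35-patient arm as base. (The actual trigger, more than 5, is 6/35 = 17.1%.) Nothing equivalent fixes the base for rules 3 and 4.

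**Single-event triggers.** Failure: 1/1 = 100% fires; 1/2 = 50% does not exceed 50%. Cross-over: 1/1, 1/2 and 1/3 = 33% all exceed 30%; 1/4 = 25% does not.

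**Inputs.** PICC failure is 10–20% (complement of 80–90% completion), midpoint 15%. LPC failure is 21% (9/43), or 35–45% from Table 2: 2 occlusions plus 5 dislodgements = 7/20, and 9/20 not kept to completion. Allocation is 35 per arm. Cross-over of 5–20% is an assumption; the documents give no rate.

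**Method.** Outcomes are taken as independent at constant rate p. Let q(n, x) be the probability of x events after n outcomes with no stop so far. Then q(n, x) = (1 − p)·q(n−1, x) + p·q(n−1, x−1), and any mass with x/n above the threshold is removed and counted as a stop.

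**Rule 3, first three outcomes in an arm.** It fires on a first failure, or on success–failure–failure: p + (1 − p)p².

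- LPC 21%: 0.21 + 0.79 × 0.0441 = 0.245
- PICC 15%: 0.15 + 0.85 × 0.0225 = 0.169
- Either arm: 1 − 0.755 × 0.831 = 0.373

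**Rule 3, all 35.** The recursion gives 0.266 and 0.176, so either arm = 1 − 0.734 × 0.824 = 0.395. As a check, the unlimited-run value is p/(1 − p): 0.21/0.79 = 0.266 and 0.15/0.85 = 0.176. So 37 of the 40 points arise within the first three outcomes of an arm.

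**Rule 3, pooled.** The mean rate is (21 + 15)/2 = 18%; 0.18/0.82 = 0.22, and the recursion over 70 agrees.

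**Timing.** 365/35 = 10.4 days between patients in an arm, against therapy of 5–14 days, so the denominator matters. Simulation used even or random arrivals, therapy length uniform on 5–14 days and failure time uniform before planned completion (all assumptions). Known-outcome figures rise because failures become known sooner than completions. The strict lag judges each outcome against one further enrolled patient.

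| Reading of rule 3 | LPC 21%, PICC 15% | LPC 45%, PICC 15% |
|---|---|---|
| Either arm, known outcomes, exact | 40% | 81% |
| Same, simulated timing | 41–48% | 82–85% |
| Either arm, enrolled patients, simulated | 31–38% | 76–80% |
| Either arm, strict one-patient lag | 10% | 60% |
| Pooled, known outcomes, exact | 22% (up to 33% simulated) | 43% |
| Pooled, enrolled patients, simulated | about 14% | 30–34% |
| Pooled, only at 20 and 40 | 0.02% | 1.8% |

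At LPC 35% and PICC 15%, exact known-outcome figures are 62% (either arm) and 33% (pooled).

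**Rule 4, pooled.** By the third subject the chance is 1 − (1 − p)³: 14%, 27% and 49% at 5%, 10% and 20%. Over all 70 it is 15%, 30% and 63%. Aim 1 counts more than 80% receiving the assigned device as success. If non-receipt were mostly cross-over (an assumption), a trial near that mark would more likely than not trip rule 4.

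**Illustrative minimum of 10.** Rule 3 per arm: 27% to 2% at 21% failure, 43% to 11% at 30%, 77% to 57% at 45%, 98% to 96% at 60%. Rule 4 pooled: 30% to 4% at 10% cross-over, 63% to 35% at 20%, 99.6% to 99.2% at 40%.

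**The case against.** The best defence is Section 6 B. It schedules review of exactly these rates after 20 and 40 enrolled, and one could read daily surveillance as covering events while rates are judged only at those reviews. Rule 3 would then almost never fire by chance. The word continuously in Section 6 C tells against this reading, but the overlap is real, and the two sections must be reconciled.

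A second defence is that early sensitivity may be deliberate. This is a paediatric trial without a DSMB, the start from the first patient is explicit, and the consequence is re-evaluation. That is a legitimate choice, but the protocol does not say that it was made. A reader might infer that a trigger ends the trial; the text supports only a stop for re-evaluation and gives no length for it.

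Third, the inputs are soft. The 43-device series was 88% PICU, 9% of its removals have no stated reason (100 − 70 − 21), two of the nine Table 2 devices not kept to completion are unexplained, and the team was working on dislodgement. This affects the sizes, not the single-event triggers.

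Finally, the cross-over passages might be read as contradictory. They can coexist: Section 6 D defines a statistic, and the risk section names the direction watched for harm. What is missing is which one rule 4 uses.

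**Conclusion.** The point holds and should be fixed. As written, rules 3 and 4 can require a stop on a single early event, and their base is undefined. At LPC 21% and PICC 15%, the chance that rule 3 fires is 10–48% across the continuous readings.

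A reader might take about 40% as the false-stop rate of this trial. The documents do not support that: it needs both per-arm judging and known-outcome denominators, and Section 6 C specifies neither. Confidence is high in the textual gap and in the single-event triggers, and much lower in any one percentage. All sizes rest on independent outcomes at constant rates; the rule 4 sizes also rest on assumed cross-over rates.

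A reader might also infer that rules 1 and 2 are faulty. They are already per-arm counts, and this point does not require rewriting them.

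**What to change.** Amend Section 6 C so that:

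- rule 3 applies only after a stated minimum number of devices have a known outcome, and rule 4 only after a stated minimum number of subjects have been randomized;
- each rule says per arm or pooled and names its denominator;
- the relation to the reviews after 20 and 40 in Section 6 B is explicit;
- rule 4 says which cross-over direction counts.

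If the sponsor wants a single early failure to pause the study, the protocol should say so. The minimum and the thresholds remain the sponsor's decision; 10 is only an illustration.

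The cost is one amended paragraph for the IRB and no new data. The price is less early sensitivity, including the fall from 77% to 57% per arm at 45% failure. Because serious complications lead to device removal under Section 6 B, rule 3 as written also catches early clots. At an assumed 30% clot rate, far above the 4.1% reported locally, rules 2 and 3 together fire by 10 patients in an arm in 41% as written and 5% with a minimum of 10. The sponsor should check that early clots and infections remain adequately covered. Daily monitoring and 24-hour IRB reporting of reportable events continue in any case.

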#### D. Describe procedures to be employed in analyzing data (including a power analysis):

Quantitative. Study data will be collected using REDCap. Feasibility outcomes will be collected from (1) screening logs maintained by the study team (rate of enrollment, assigned intervention), (2) ease/difficulty of VAD placement (scale 0=worse to 10=best) to determine VAD acceptability, and (3) REDCap datasheet for assessing missed data. Patient demographics (age, gender, race/ethnicity), clinical factors (reason for admission, co-morbidities, reason for PICC/LPC request, therapy to be infused, requesting service, hospital floor), VAD data (VAD type and size placed, insertion site/vessel, sedation, number of attempts, additional VADs), effectiveness data (time-to-removal of VAD, prolonged NPO, number of lab draws from VAD, number of non-VAD blood draws) and complications requiring medical intervention will be collected using the EMR and daily (Monday-Friday) check-ins with the bedside nurse. Procedural pain with non-sedated VAD placement will be assessed in patients age > 5 years by the RC within 24 hours of insertion using the Faces Pain Score (FPS) or the 0-10 pain scale depending on the developmental age of the patient. Patient/parent anxiety and overall experience with VAD placement will be assessed on a 0-10 scale (0= lowest, 10=highest) and using the short State-trait anxiety inventory (STAI) that is validated in children 5 and older.

Descriptive statistics will be used to report feasibility outcomes and explore clinical factors (see above). Cross over rate will be calculated as the proportion of the number of subjects who crosses from the randomized arm/line to a different arm/line. The exact Clopper-Pearson 95% confidence interval will be generated. Time-to-device removal for all reasons will be compared using a t-test. Non-inferiority of LPCs to PICCs will be demonstrated if the 95% confidence interval of the mean difference lies above -1 (non-inferiority margin: 1 day). The remaining outcomes will be compared using Chi-square test or Fisher's exact for categorical variables and t-test or Mann-Whitney-Wilcoxon test for continuous variables. Where necessary for parametric assumptions, appropriate transformations will be employed. Non-parametric tests will be used where parametric assumptions are not satisfied. Logistic regression or general linear model will be performed to control the potential confounders.

The study is not powered to detect statistical significance, but rather to assess the feasibility of this study protocol for a larger full-scale effectiveness trial and provide baseline estimates for the sample size calculations. With a sample size of 60 or more patient subjects, we will be able to estimate a participation rate of 70% (eligible patients agree to enrollment and randomization) within a 95% confidence interval of +/- 12%.

Qualitative. We will perform semi-structured interviews in a subgroup of the study participants; the adult guardians will be asked to participate as research subjects. We anticipate interviewing up to 35 participants from each randomized study group (70 total), but sample size will be determined by data saturation. Interviews will be completed by the research team within the week following completion of therapy, either in person (if the patient is still hospitalized) or via phone (if the patient was discharged). The main purpose of the interviews is to understand the patient's and family's lived experience with device insertion and ongoing maintenance during the time of participation in the study. The child is welcome to participate in the interview with their adult guardian but not required to. Their advice on ways to improve the process of insertion and/or maintenance will be collected as well. Interviews will be audio-recorded, transcribed verbatim, and uploaded into MAXQDA Qualitative Analysis software for coding. We will use a team-based inductive coding strategy, followed by theme identification.

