#### C. Hypothesis/specific aims:

The aims of this pilot, randomized controlled trial are:

*Aim 1:* To assess the feasibility of a full-scale effectiveness trial comparing PICCs to LPCs in hospitalized pediatric patients in need of non-central, medium-term vascular access (5-14 days anticipated need). *Hypothesis:* Feasibility of a full-scale effectiveness trial will be established by demonstrating that > 70% of eligible patients agree to enrollment and randomization, > 80% of randomized patients receive the assigned intervention, > 80% of providers involved find the study acceptable, and < 5% of data are missing.

*Aim 2*: To identify a population in which a LPC is a safe and effective alternative to a PICC for vascular access in hospitalized pediatric patients age > 2 years, in need of non-central, medium-term access. *Hypothesis:* We hypothesize that LPCs are non-inferior to PICCs for delivery of peripherally compatible infusate needed for 5-14 days in hospitalized pediatric patients. We plan to determine the time-to-removal of the vascular access device, both secondary to completion of therapy and secondary to complications. Safety will be assessed by measuring complication rate (e.g., VTE, CLABSI, occlusion, dislodgement, phlebitis). Cross over rate will be closely monitored as well.

*Aim 3:* To engage patients and families as advisors in vascular access device selection. We will describe the patient and family experience with device placement and maintenance as well as perceived patient and parent insertion-related and sedation-related distress.

D. Background, significance, and rationale (including description of preliminary studies and any results):

Many hospitalized children require a vascular access device (VAD) for delivery of life saving interventions such as intravenous fluids and antibiotics.[1] With the broad range of VADs available, and their different profile of complications,[2] it is essential that clinicians have access to rigorous evidence to guide the selection of the most appropriate VAD. Appropriate VAD selection results in treatment efficiency and a decrease in catheter-related complications.[1] The problem is, even the most current and comprehensive guideline for VAD selection published in 2020, the Michigan Appropriateness Guide for Intravenous

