#### A. Is a Data Safety Monitoring Board (DSMB)/Data Monitoring Committee (DMC) in Place?

#### ⊠No □ Yes □ N/A (study is not greater than minimal risk)

**If YES**, describe its members and how often they meet (you may include any DSMB/DMC charters in the submission package; once the study has been opened locally any DSMB/DMC reports should be submitted for review as reportable new information):

B. If there is no formal DSMB/DMC, describe the monitoring plan or indicate that the study involves no more than minimal risk (if the IRB disagrees and determines the study to be greater than minimal risk, the study will be deferred until an appropriate monitoring plan has been developed):

[name] (PI) will oversee the continuous monitoring of participant. She will accurately report any deviation from the protocol and identify adverse events. Monthly in person or zoom meeting with the research team will be conducted to discuss everything from the study enrollment to outcomes to safety monitoring and overall study progress.

Complications related to the two VADs will be monitored daily on-site while participants are hospitalized, and it is one of the main outcomes of the study. Safety assessment including analysis of complication rates, catheter failure

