rate and cross-over rate will be conducted after enrolling 20 and then again after enrolling 40 out of the 70 participants. Participants' length of hospitalization is not dependent on the study participation and discharge criteria will be determined by their primary medical team. In case of a serious complication related to the VADs, the planned rescue intervention is to remove the VAD and treat the complication per routine clinical care. The primary attending physician will guide treatment of any catheter related complications in collaboration with the treating team. Treatment of catheter-related complications will not be the responsibility of the research team. Both VADs included in this study are regular standard of care at Children's Wisconsin, and treating their complication falls within the responsibility of the primary medical provider taking care of that patient. A comprehensive list of catheter related complications [36] are provided in the table below. Some of the complications (e.g., phlebitis and infiltration) are graded based on severity following established guidelines per the Infusion Therapy Standards of Practice.[36] Complications are divided into major (serious complications that generally require treatment) and minor complications (less serious complication that don't generally require treatment).

The proposed study is a feasibility pilot trial and not powered to detect a difference in efficacy between groups, therefore, efficacy stopping rules can't be established. See safety stopping rules below.

Complications	Definition
Major	·
Central line associated bloodstream	NHSN surveillance definition: A laboratory confirmed infection
Infection (CLABSI)	where a LVC is in place for >2 calendar days prior to a positive
	culture
Catheter-associated blood stream	A bloodstream infection (BSIs) originating from either
infection (CABSI)	peripheral intravenous catheters (PIVCs) and/or central
	vascular access devices.
Catheter- related blood stream	It is diagnosed if the same organism is isolated from a
infection (CR-BSI)	blood culture and the tip culture, and the quantity of
	organisms isolated from the tip is greater than 15 colony
	forming units (CFUs). Alternatively, differential time to
	positivity (DTP) requires the same organism to be isolated
	from a peripheral vein and a catheter lumen blood culture,
	with growth detected 2 nours sooner (ie, 2 nours less
	incubation) in the sample drawn from the catheter.

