Catheter-related venous	Positive clot on imaging (ultrasouna) at catheter site.
Minor	
Infiltration /Extravasation	The fluid being infused leaks out into of the yein into the
	surrounding tissue ("tissuing") Graded 1-A on the bases of
	increased severity
Dislodgement	Catheter accidentally comes out.
Occlusion	Inability to flush the catheter.
Mechanical failure	Catheter fracture, mispositioning, kinking.
Leaking	The fluid being infused leaks out of the exposed catheter part
	into the surrounding environment
Phlebitis	Pain and erythema/swelling at the site of catheter. Graded 1-
	5 on the basis of increased severity.

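### Section 6 D collects only complications that need an undefined medical intervention, so minor events with neither treatment nor device removal could be missing from the Aim 2 complication rate

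*Combined protocol and SAP*

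**What the plan says.** Section 6 D (data analysis procedures) lists the variables to be collected. Its only complication item reads: "complications requiring medical intervention will be collected using the EMR and daily (Monday-Friday) check-ins with the bedside nurse". The documents do not define what counts as a medical intervention, and the collection form is not among them.

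Other places describe complications without that limit:

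- Section 1 C, Aim 2: "Safety will be assessed by measuring complication rate (e.g., VTE, CLABSI, occlusion, dislodgement, phlebitis". The same aim asks for "time-to-removal of the vascular access device, both secondary to completion of therapy and secondary to complications".
- Section 6 B, monitoring plan: "Complications related to the two VADs will be monitored daily on-site while participants are hospitalized, and it is one of the main outcomes".
- Section 6 B, complication table: "Complications are divided into major (serious complications that generally require treatment) and minor complications (less serious complication that" generally do not need treatment. The table lists six minor types. Infiltration/extravasation and phlebitis carry severity grades. Occlusion is defined simply as "Inability to flush the catheter".
- Section 6 B, scheduled safety analyses: complication rates are reviewed together with the catheter failure "rate and cross-over rate will be conducted after enrolling 20 and then again after enrolling 40 out of the 70 participants".

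**The concern.** The plan defines and grades a class of events that it expects mostly to go untreated. The sentence that decides what enters the dataset then selects on intervention. A coordinator or database builder working from Section 6 D could properly omit a grade 1 phlebitis or a small leak, although the Section 6 B table counts both as complications.

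Two things are at stake. First, the complication rate is the Aim 2 safety measure and is analysed after 20 and 40 participants. Without these events it would be too low, and the lower grades of phlebitis and infiltration would be missing. Second, because the qualifier is undefined, staff could apply it differently from one patient to the next. Section 6 D also says that the pilot should supply baseline estimates for planning the full-scale trial, so an incomplete rate could be carried forward.

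**Working it through.** No figure in the plan depends on this sentence, so the main check is to compare the sections and ask which events have another route into the data.

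**Other routes in the plan.** Section 6 D collects time-to-removal and additional devices. Aim 2 needs removals caused by complications. Stopping rule 3 in Section 6 C needs every removal before completion of therapy. Section 6 B treats removal as an intervention, at least for serious events: "In case of a serious complication related to the VADs, the planned rescue intervention is to remove the VAD". Section 8 E says which common events lead to replacement of the device.

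| Minor complication (Section 6 B) | Route into the data other than the complication item |
|---|---|
| Dislodgement | The catheter is out by definition, so time-to-removal captures it |
| Occlusion | Section 8 E says replacement follows in both arms; if it is cleared in place, the clearing may itself count as an intervention |
| Mechanical failure | Section 8 E says replacement follows for PICCs; nothing is said for LPCs |
| Infiltration/extravasation | Section 8 E says replacement follows for LPCs; a mild event with the device left in place has no route |
| Leaking | None stated if the device stays in and nothing is done |
| Phlebitis | None stated for low grades if the device stays in and nothing is done |

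The gap is therefore mainly low-grade phlebitis, mild infiltration and leaking.

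**What the local data show (Section 1 D).**

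- First LPC series, phlebitis: 0 of 20. The exact two-sided 95% upper limit is 1 − 0.025^(1/20) = 0.168, or about 17%.
- First LPC series, other minor events: 5 dislodgements + 2 occlusions = 7, while 20 − 11 = 9 catheters did not last until therapy was complete. Nine is enough to contain all 7, but the table does not link them.
- Later LPC series: 9 of 43 (21%) were removed for complications. Complications appear there only as reasons for removal, so the series cannot show how many events occurred without removal.
- Neither series gives a rate for leaking or mild infiltration without removal, and neither covers PICCs.

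**Scale only.** With 35 per arm, one patient whose only complication is unrecorded lowers that arm's any-complication rate by 1/35 = 2.9 percentage points. With equal arms (assumed), the step is 1/20 = 5 points at 40 enrolled and 1/10 = 10 points at 20 enrolled. These are the effects of one missed patient and are not evidence that any would be missed.

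**Analyses that do not use the item.** The non-inferiority test uses time-to-removal. Stopping rules 1 and 2 concern bloodstream infection and thromboembolism, which Section 8 E says need medical treatment and removal. Rules 3 and 4 concern early removal and cross-over.

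**The case against.** The strongest reply is that Section 6 D is shorthand in a list of data sources and that Section 6 B governs safety. Section 6 B promises daily monitoring and a comprehensive list, and grading phlebitis and infiltration makes sense only if low grades are recorded. The first local series gave phlebitis its own row with no stated filter, which suggests that this team tabulates such events anyway. Generally needing no treatment is also not the same as needing no intervention, and the commonest minor events lead to replacement. Finally, this is a feasibility pilot, the filter applies to both arms, and the overall complication rate triggers no decision.

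Much of this stands. It narrows the gap and makes the loss conditional on how the form is built. It does not remove the qualifier from the only itemised collection list, and if the intention is to record everything, the amendment simply says so.

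A reader might infer that the LPC complication rate could fall from 7/20 = 35% to zero, because every event in the first series was of a minor type. The documents do not support that: all 7 were dislodgements or occlusions, and those have the other routes shown above. A reader might also infer a bias in favour of one arm, since Table 1 in Section 1 D lists infiltration for LPCs only. The documents give no rate of untreated events by arm, so no direction can be claimed.

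**Conclusion.** The mismatch in wording is real. If Section 6 D is followed literally, the Aim 2 complication rate omits events with neither treatment nor removal and is understated to that extent. This rests on two assumptions: that the collection form follows Section 6 D, and that removal counts as an intervention or is captured elsewhere. If removal did not count and its cause were not recorded, the gap would be wider, but Aim 2 and stopping rule 3 make that unlikely.

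Neither the number of events lost nor the effect on the comparison between arms can be calculated from the documents. The finding concerns the completeness of a descriptive safety outcome. It should be corrected, but it does not call the design or the non-inferiority analysis into question.

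**What to change.** In Section 6 D, replace the qualified complication item with: *all major and minor complications in the Section 6 B table, in both arms, with grade where graded, and whether treatment or device removal followed*. State that the Aim 2 complication rate is calculated from these records. Complications leading to treatment or removal may then be reported as a subset, which keeps the narrower measure available if the investigators want it.

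The cost is one replaced phrase, one added sentence, a few more REDCap fields and slightly more data entry. The record review and bedside-nurse check-ins are already planned. The documents do not say whether low-grade events are routinely charted with a grade, so the nurse may need to be asked for it at the check-in.
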